6.6. SOFTWARE VERSION

All analyses will be conducted using SAS version 9.2 or higher.

7. STATISTICAL CONSIDERATIONS

7.1 ADJUSTMENTS FOR COVARIATES AND FACTORS TO BE INCLUDED IN ANALYSES

The following factors are used in the analyses. For details of their inclusion in the models, see section 15.1.3.

- Treatment (Study medication and matching placebo tablets)
- Dose visit (Visit 2 and Visit 3)
- Subject
- Treatment sequence (Group A: Patients take study medication at Visit 2 and matching placebo tablets and Visit 3. Group B: Patients take study medication at Visit 3 and matching placebo tablets at Visit 2).

7.1. MULTICENTER STUDIES

This study will be conducted at two or more hospital sites. The 4-hour pH endpoints will be summarized separately for each center. Center will not be included as a factor in any of the statistical models because the study has a cross-over design

7.2. MISSING DATA

Patients who withdraw from the study will not be replaced.

Unless otherwise specified, all analysis will be based on the number of non-missing observations, i.e. patients with missing information will not be included in the denominator when calculating percentages. If relevant for categorical tabulations, missing values will be treated as another category, so that all tabulations involving this variable will also include a row or column as appropriate to indicate the number of patients for whom the variable was recorded as a missing value.

For AEs, partial or missing dates and times will not be imputed, and this will be listed as originally reported in the Case Report Form (CRF).

7.3. EXAMINATION OF SUBGROUPS

No subgroup analyses will be performed for this study.

Document: Reckitt Benckiser GA1202 Statistical Analysis Plan

Author: [REDACTED]

Version Number:

Final 5.1

Version Date:

[25Feb2014]

Template No: CS_TP_BS016 – Revision 3

Effective Date: 01May2012

Reference: CS_WI_BS005

Page 12 of 29

7.4. MULTIPLE COMPARISONS/ MULTIPLICITY

Since there is only one primary analysis, no multiple comparison adjustments will be used.

8. OUTPUT PRESENTATIONS

The table and listing templates provided with this SAP describe the conventions for presentation of data in outputs, and presentations for this study and therefore the format and content of the summary tables, figures and listings to be provided by Quintiles Biostatistics.

9. DISPOSITION AND WITHDRAWALS

The number of patients who provided informed consent, as well as those who were eligible at Visit 1 and Visit 2 (met all inclusion criteria and not met all exclusion criteria) will be summarized overall. The number of patients who completed the study, the number of patients who withdrew prematurely from the study, the reasons for withdrawals and the number of patients in the FAS, Safety, ITT and PP population (see Section 4 for population definitions) will be summarized for each treatment sequence group and overall. Listings on patient completion/withdrawal information, as well as eligibility details will be reported

Major protocol violations will be summarized by treatment sequence group and overall. Furthermore the number of patients to be excluded from each population together with reasons of exclusion will be summarized. Details on major protocol violations as well as population classification information will be listed.

10. DEMOGRAPHIC AND OTHER BASELINE CHARACTERISTICS

Demographic data and other baseline characteristics will be summarized by treatment sequence group and overall for all patients in FAS.

No statistical testing will be carried out for demographic or other baseline characteristics.

The following demographic and other baseline characteristics will be reported for this study:

- Age (years) – calculated relative to date of consent
- Race
- Sex
- Height
- Weight

Counts and percentages will be displayed for patients with smoking habits (no, yes, former), alcohol/drug use (no, yes) and drugs of abuse history; summary statistics (mean, median, minimum, maximum and standard deviation) will be provided for the continuous variables including height, weight, age, smoking/drinking years and amount. These data will also be listed.

Document: Reckitt Benckiser GA1202 Statistical Analysis Plan

Author: [REDACTED]

Version Number:

Final 5.1

Version Date:

[25Feb2014]

Template No: CS_TP_BS016 – Revision 3

Effective Date: 01May2012

Reference: CS_WI_BS005

Page 13 of 29

Summary statistics will be presented for patients' baseline Gastro-esophageal reflux disease (GERD) symptoms, including the severity and frequency of heartburn. In addition, 12 lead ECG and a standard hospital endoscopy examination will be conducted at baseline as part of the screening procedures. The following Information on ECG and endoscopy will be presented by summary statistics:

ECG:

Whether ECG is performed

Interpretation of ECG results

Endoscopy:

Whether endoscopy performed

Whether local anaesthetic throat spray administered

Whether a sedative administered

Any abnormalities presented in endoscopy

If the patient has erosive GERD

If the patient have hiatus hernia and diameter of the hernia

Other baseline characteristics such as laboratory evaluations, vital signs, and physical examination are specified in section 16.3, 16.5 and 16.6 respectively.

10.1. DERIVATIONS

Age = Date of Informed Consent – Date of Birth (rounded down to the nearest whole year)

11. MEDICAL HISTORY

Medical History conditions are defined as those conditions which stopped prior to or at screening visit. Medical history information will be coded using version 16.0 of Medical Dictionary for Regulatory Activities (MedDRA) coding dictionary and presented for all patients in FAS by system organ class (SOC) and preferred term (PT), for each treatment sequence group and overall.

12. CONCOMITANT ILLNESSES

Concomitant illnesses are conditions other than GERD which are ongoing before or on the day of last dose of Investigational Medicinal Product (IMP), or stopped after screening visit but before or on the day of last dose of IMP. Concomitant Illnesses will be captured from Medical History and Current Status form in CRF, and will be coded using MedDRA version 16.0 and presented for all patients in safety population by SOC and PT, for each treatment sequence group and overall.

Document: Reckitt Benckiser GA1202 Statistical Analysis Plan

Author: [REDACTED]

Version Number:
Version Date:

Final 5.1
[25Feb2014]

Template No: CS_TP_BS016 – Revision 3

Effective Date: 01May2012

Reference: CS_WI_BS005
Page 14 of 29

13. PRIOR AND CONCOMITANT MEDICATION AND THERAPIES

Medications will be coded using World Health Organization (WHO) Drug Dictionary Enhanced version dated 01Mar2013 and tabulated using the Anatomical Therapeutic Chemical (ATC) classification system, under Level 3 and Level 4 for the FAS (for prior and concomitant medications separately)

- 'Prior' medications are medications which started and stopped prior to first dose of study medication.
- 'Concomitant' medications are medications which:
 - o started prior to, on or after first dose of study medication
 - o AND ended on or after first dose of study medication or were ongoing at the end of the study.

14. STUDY MEDICATION EXPOSURE & COMPLIANCE

At each of the pH monitoring visits, patients will be administered four Compound Sodium Alginate Double Action Chewable Tablets or four matching placebo tablets under the supervision of the Investigator or his or her delegate. No measurement on medication compliance will be performed.

In addition, all patients will then receive Compound Sodium Alginate Double Action Chewable Tablets (two tablets four times daily) as Non-investigational Medicinal Product (NIMP) for symptomatic treatment. The number of tablets dispensed and returned will be recorded in CRF and presented by table and listing.

The following information regarding whether the patients fulfill each requirement prior to pH monitoring and the time interval from each procedure to taking treatment will be summarized by treatment sequence group:

Requirement prior to pH monitoring:

Not taken symptomatic treatment for GERD (antacids etc) in the 24 hours prior to pH monitoring

Abstain from alcohol 24 hours prior to the test meal

Fast for a minimum of 4 hours prior to insertion of manometry probe

Insert manometry probe to aid positioning of esophageal pH sensor prior to consuming test meal

Consume the entire reflux provoking meal

Record pH from 30 minutes prior to dosing to 4 hours post dosing

Time interval from each procedure to taking treatment:

Position pH electrode (90 mins before treatment)

Eat test meal (60 mins before treatment)

Activate pH monitoring data logger and Record (30 mins before treatment)

Stop pH monitoring (4 hour post dose)

The calculation of time interval is provided in section 14.1

Document: Reckitt Benckiser GA1202 Statistical Analysis Plan

Author: [REDACTED]

Version Number:

Final 5.1

Version Date:

[25Feb2014]

Template No: CS_TP_BS016 – Revision 3

Reference: CS_WI_BS005

Effective Date: 01May2012

Page 15 of 29

14.1. DERIVATIONS

Time interval from each procedure to taking treatment (minutes) is calculated by

- Time of the procedure – Time when patient takes treatment

15. EFFICACY OUTCOMES

15.1. PRIMARY EFFICACY

15.1.1. PRIMARY EFFICACY VARIABLE

The primary efficacy endpoint is the percentage of time during the 4 hour post dosing period with pH below pH 4 for Compound Sodium Alginate Double Action Chewable Tablets versus matching placebo tablets. This variable is collected on the “Results of 4-hour pH Monitoring” page in CRF.

15.1.2. MISSING DATA METHODS FOR PRIMARY EFFICACY VARIABLE

If less than 2 hours post-dosing monitoring result for this variable is available, for whatever reason, the derived variable will be considered missing. If 2 or more hours post-dosing monitoring data is available, the parameter will be derived by multiplying by the factor (4 hours / time with data available). Any data recorded more than 4 hours post-dosing will be ignored when deriving these parameter.

The table below shows the implementation of adjustment rules under different monitoring duration scenarios.

Monitoring Duration(End of pH monitoring – taking treatment)	Percentage of time with pH<4 during the monitoring period (data directly from database)	Number of hours with pH<4 during the monitoring period	Adjustment factor	Adjusted percentage with pH<4 over 4 hours
240 mins (4 hours)	80.0%	240 mins	1	80.0%
230 mins (<4 hours)	80.0%	230*80% mins	240/230	230*80%*240/230/240=80.0%
90 mins (<2 hours)	20.0%	90*20% mins	NA	missing

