14.4 Efficacy Analyses

Results will be summarised by treatment for each dosing visit and overall (Compound Sodium Alginate Double Action Chewable Tablets, matching placebo tablets) using n, mean, standard deviation, median, minimum and maximum values.

If less than 2 hours post-dosing monitoring data is available, for whatever reason, (or less than 1 hour post-dosing data within the first hour for parameters based on the first hour post-dosing) the derived parameters will be considered missing. If 2 or more hours post-dosing monitoring data is available, the parameters will be derived using the data available, and will be adjusted, where necessary, by multiplying by the factor (4 hours / time with data available). Any data recorded more than 4 hours post-dosing will be ignored when deriving these parameters.

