15.2.2 MISSING DATA METHODS FOR SECONDARY EFFICACY VARIABLES

Missing data for the percentage of time during the 4 hour post dosing period with pH below pH 5 due to early termination of recording will be derived in the same way as for the primary efficacy variable.

For the following secondary efficacy variables:

- Number of occasions during the 4 hour post dosing period when pH falls below pH 4
- Number of occasions during the 4 hour post dosing period when pH falls below pH 5
- Number of reflux episodes during the 4 hour post dosing period with pH below pH 4 for at least 5 minutes

If less than 2 hours post-dosing monitoring result for these variables is available, for whatever reason, the derived variable will be considered missing. If 2 or more hours post-dosing pH data is available then the variable will be multiplied by 4 / (hours of post-dosing pH data available). Any data recorded more than 4 hours post-dosing will be ignored when deriving these parameters.

The table below shows the implementation of adjustment rules (take number of occasions as an example) under different monitoring duration scenarios.

Monitoring Duration(End of pH monitoring – taking treatment)	Number of occasions with pH<4 during the monitoring period (data directly from database)	Adjustment factor	Adjusted occasion with pH<4 over 4 hours
240 mins (4 hours)	2	1	2
230 mins (<4 hours)	2	240/230	2*240/230=2.09
90 mins (<2 hours)	1	NA	missing

Missing data for other secondary endpoints due to early termination of recording will not be derived.

Document: Reckitt Benckiser GA1202 Statistical Analysis Plan

Author:

Version Number:

Final 5.1

[25Feb2014]

Template No: CS_TP_BS016 – Revision 3

Effective Date: 01May2012

Reference: CS_WI_BS005

Page 18 of 29

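### The sentence in SAP 15.1.2 that derives the primary percentage from a short pH trace conflicts with the SAP's own worked table; the table's method is the valid one, and one cell of it needs correcting

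*SAP*

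**What the plan says.** SAP 15.1.1 defines the variable: "The primary efficacy endpoint is the percentage of time during the 4 hour post dosing period with pH below pH 4". It is read from the CRF page of pH monitoring results, and the table in 15.1.2 labels the percentage as coming straight from the database for the period monitored.

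SAP 15.1.2 sets a floor: "If less than 2 hours post-dosing monitoring result for this variable is available, for whatever reason, the derived variable will be considered missing". Above that floor, "the parameter will be derived by multiplying by the factor (4 hours / time with data available"). A worked table follows, introduced as the implementation of the rule. For a 230-minute trace at 80% its final cell reads "230*80%*240/230/240=80.0" per cent. Its first row, for a monitoring duration of "240 mins (4 hours"), shows 80.0% observed, 240 minutes with pH below 4, a factor of 1 and an adjusted 80.0%.

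SAP 15.1.3 uses the data adjusted in this way for the primary ITT analysis. SAP 15.2.2 handles 4-hour time below pH 5 in the same way, multiplies three 4-hour counts by the same factor, and then states: "Missing data for other secondary endpoints due to early termination of recording will not be derived".

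Protocol 14.4 (and 3.11) covers the 4-hour parameters together: they "will be adjusted, where necessary, by multiplying by the factor (4 hours / time with data available").

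**The concern.** The sentence and the table give different values for the same trace. The sentence applies the factor to the parameter, which 15.1.1 has just defined as a percentage. It mentions neither a conversion to minutes nor a division by 240, and those are the two steps that make the table come out right.

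The literal reading is a realistic one. In 15.2.2 almost the same instruction, given for counts, does mean multiplying the database value directly. A programmer could reasonably carry that over to the percentage.

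At stake is the derivation of the primary endpoint, and of time below pH 5, for short traces. The inflation would fall on the visit with the short trace, so it would distort that patient's within-patient contrast, on which a crossover analysis depends.

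**Working it through.** **Inputs.** Full period 240 min and minimum usable trace 120 min (SAP 15.1.2), so the factor 240/T is at most 240/120 = 2. The 80% and 20% values and the 230-minute duration are the SAP's illustrations. The 180- and 120-minute durations and the 50% value are my assumptions; both durations lie within the permitted range. T is minutes recorded and p is the observed percentage of T.

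**1. The SAP's own figure (table method).** Minutes below pH 4 = T × p = 230 × 0.80 = 184. Scaled: 184 × 240/230 = 192. As a share of 240: 192/240 = 80.0%. The table's result reproduces. In general (T × p) × (240/T) / 240 = p, so the method returns the observed percentage at any duration and cannot exceed 100%.

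**2. The sentence applied to the percentage.** Adjusted value = p × 240/T.

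| T (min) | p | Sentence | Table method |
|---|---|---|---|
| 230 | 80% | 80 × 240/230 = 83.48% | 80% |
| 180 | 80% | 80 × 240/180 = 106.67% | 80% |
| 120 | 80% | 80 × 240/120 = 160% | 80% |
| 120 | 50% | 50 × 240/120 = 100% | 50% |
| 120 | 20% | 20 × 240/120 = 40% | 20% |

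The sentence gives more than 100% whenever p is above T/240: above 120/240 = 50% at 120 min, 180/240 = 75% at 180 min, and 230/240 = 95.83% at 230 min.

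**3. Row 1 of the table.** Rows 2 and 3 compute minutes as duration × percentage. For row 1 that is 240 × 0.80 = 192, not the printed 240; 240 of 240 minutes would be 100%. With 192 the row is consistent: 192 × 1/240 = 80.0%, the adjusted value already printed.

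**4. Counts in 15.2.2.** 2 × 240/230 = 2.09, as the SAP prints. A count has no recorded time in its denominator, so direct scaling is coherent there.

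**5. What one misderived trace could do (illustration).** Assume 36 completers, 18 per sequence, and one patient at 50% on both visits with a 120-minute trace at one of them. The sentence turns 50% into 100%, a false within-patient difference of 50 points. The treatment estimate is half the difference between the two sequence means of the within-patient differences, so it shifts by 50/18/2 = 1.39 points.

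**The case against.** The strongest reply is that the SAP already prescribes the right number. The table follows directly on the sentence, is offered as its implementation, and gives the same value as minutes below threshold over minutes recorded. The primary objective is also framed as time rather than percentage, so the sentence can be read as scaling time with the later steps left out. This stands in large part: anyone who follows the table gets a valid percentage. It does not rescue the sentence, which taken alone gives a different value for the SAP's own example.

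The row 1 slip has no numerical effect. The percentage comes from the database, the factor is 1, and the printed 80.0% is correct. That too stands, though the example meant to settle the wording should be free of errors.

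A reader might infer that the protocol requires every 4-hour parameter to be scaled, including longest reflux time, and that the SAP quietly drops this. The documents do not support either step. The protocol makes the adjustment conditional on need, as the quoted words show. SAP 15.2.2 says openly that the remaining secondary endpoints are not derived for short recordings, and protocol section 14 expects departures from its analyses to be set out in the SAP.

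Short traces may also be few, since patients stay in the clinic under supervision. The per-protocol analysis requires complete 4-hour data at both visits. The complete-case analysis is less protection, because it runs only if more than 10% of patients lack a 4-hour recording (within 5 minutes).

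**Conclusion.** The point holds as an inconsistency between the derivation sentence for the primary endpoint and its worked example, plus one wrong illustrative cell. For the SAP's own case the gap is 83.48% against 80.0%, or 3.48 points. It would be larger for shorter traces, with values above 100% once the observed percentage exceeds T/240.

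These sizes rest on a literal reading of the sentence and, apart from the 230-minute case, on assumed durations. A reader might infer that the trial's results contain inflated or impossible percentages. The documents do not show this: the table's method cannot produce them, and nothing in the plan says how many traces were short or which instruction was programmed. Bias follows only if the sentence was used in place of the table. The point is worth correcting because it concerns the primary endpoint and the remedy is simple.

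**What to change.** In SAP 15.1.2, replace the multiplication sentence with a direct definition: the percentage equals minutes below the threshold divided by minutes recorded within 0 to 240 minutes after dosing, with no further scaling, and is missing if fewer than 120 minutes were recorded. Apply this to pH below 4 and, through 15.2.2, to 4-hour time below pH 5. Correct the row 1 minutes cell to 192.

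In SAP 15.2.2, keep the 4/t factor for the three counts only. State that longest reflux time and DeMeester score are not scaled, and whether their values from a short trace are used as recorded or left missing.

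Protocol 3.11 and 14.4 can stand, given their conditional wording, provided the SAP says that its own rule governs. The cost is SAP wording only: no new data and no change to the design or the analysis model. If outputs have already been produced, check the derivation code for any trace under 240 minutes.

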15.1.3 PRIMARY ANALYSIS OF PRIMARY EFFICACY VARIABLE

The primary endpoint will be analysed primarily using a linear mixed model with treatment, dosing visit and

Document: Reckitt Benckiser GA1202 Statistical Analysis Plan

Author: [REDACTED]

Version Number:

Final 5.1

Version Date:

[25Feb2014]

Template No: CS_TP_BS016 – Revision 3

Effective Date: 01May2012

Reference: CS_WI_BS005

Page 16 of 29

treatment sequence as fixed effects and patient nested within treatment sequence as a random effect. The primary analysis is to test the null hypothesis that there is no difference between treatment, Least square means (with 95% CI) corresponding to the two treatments will be presented. Descriptive statistics will also be presented for the primary endpoint by treatment for each dosing visit and overall. The effects for dosing visit and treatment sequence will also be assessed.

The following SAS core code will be used.

```
proc mixed data=XXX method=REML;
  class treatment visit sequence subID;
  model Y= treatment visit sequence /ddf=kenwardroger;
  random subID(sequence);
  lsmeans treatment/diff cl;
run;
```

SAS output from Mixed procedure will be sent to the sponsor to assist with the model assumptions review.

The linear mixed model for the primary endpoint is based on the assumption that the percentage of time with pH<4 within each treatment sequence group is normally distributed. To test this assumption, a qualitative residual analysis will be performed. If there is a major departure from the assumptions of normality or heteroscedasticity of residuals, then further analysis using transformed data might be performed if deemed necessary. If the analysis based on the transformed data still rises reasonable concerns about validity of the tests then the Wilcoxon Rank-Sum test will be used to compare the dosing visit difference (dosing visit 1 – dosing visit 2) between treatment sequence groups to represent the treatment comparison.

The primary efficacy analysis will be performed for the ITT population using adjusted 4-hour data based on the imputation rule specified in section 15.1.2.

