14.4.3 Statistical Methods for Efficacy Analyses

SAS 9.1 (or later) will be used for statistical analysis.

All statistical tests will be conducted using two-tailed tests at the 5% significance level.

The null hypothesis at all times will be the equality of the fixed effect being compared from the model.

The primary endpoint will be analysed primarily using an ANOVA of variance model with treatment, dosing visit treatment sequence as fixed effects and patient nested within treatment sequence as a random effect. The difference between treatment least square means will be used to represent the treatment differences. The effects for dosing visit and treatment sequence will also be assessed. A residual analysis will be performed. If there is a major departure from the assumptions of normality, independence or heteroscedasticity of residuals, then further analysis using transformed data will be used to support the original model results. If such assumptions still do not hold following an appropriate transformation then Wilcoxon Rank-Sum test will be used to compare the dosing visit difference (dosing visit 1 – dosing visit 2) between treatment sequence groups to represent the treatment comparison.

All secondary endpoints will be analysed identically to the primary endpoint.

All secondary endpoints and sensitivity or alternate analyses for the primary endpoint will serve as supportive evidence for the primary analysis only and therefore no adjustment for multiple comparisons will be made.

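### SAP 15.1.3 shows the sponsor the treatment result during the assumptions review and omits the protocol's supportive-only wording, leaving an avoidable opening for a result-aware choice of test

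*SAP*

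**What the plan says.** **SAP 15.1.3.** "The primary endpoint will be analysed primarily using a linear mixed model" with treatment, visit and sequence as fixed effects and patient within sequence as random. The printed core code contains "lsmeans treatment/diff cl". Directly after the code comes: "SAS output from Mixed procedure will be sent to the sponsor to assist with the model assumptions review". The residual review is described as qualitative, with no threshold. If there is a major departure from assumptions, "further analysis using transformed data might be performed if deemed necessary". If the transformed analysis "still rises reasonable concerns about validity of the tests then the Wilcoxon Rank-Sum test will be used" on the visit differences between sequence groups, to stand for the comparison of treatments.

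**Other SAP sections.** Section 4 places the analyses after database lock. Section 6.5 allows a log or some other transformation after the data have been inspected, decided jointly with the sponsor. Section 7.4 says there is a single primary analysis. Section 15.1.4 gives sensitivity status to the per-protocol and complete-case analyses. It does not mention the transformed or Wilcoxon analyses.

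**Protocol 14.4.3.** After a major departure, "further analysis using transformed data will be used to support the original model results". The fallback beyond that is worded without discretion: "If such assumptions still do not hold following an appropriate transformation then Wilcoxon Rank-Sum test will be used", again on the visit differences. The section ends by saying that secondary endpoints and "sensitivity or alternate analyses for the primary endpoint will serve as supportive evidence for the primary analysis only".

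**The concern.** The assumptions review is the gate to the next analysis. The people carrying it out receive the treatment difference and its limits in the same output, and every later step depends on judgement. The sentences in the protocol that keep the later analyses supportive are not in SAP 15.1.3 or 7.4. A reader holding only the SAP learns that Wilcoxon will be used once concerns remain, but not whether it then replaces the mixed model or sits beside it.

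What is at stake is the 5% level of the primary test. If one test is fixed in advance, the level holds. If the choice could follow the result, it would not.

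**Working it through.** **1. Wording side by side**

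| Step | Protocol 14.4.3 | SAP 15.1.3 |
|---|---|---|
| Deciding model | ANOVA model, named as the primary method | Mixed model, named as the primary method |
| Transformed data | Will be used, in support of the original model | Might be performed, if judged necessary |
| Trigger for Wilcoxon | Assumptions still not met | Reasonable concerns about validity |
| Status of alternate analyses | Supportive only | Not stated |
| Material for the review | Residual analysis | MIXED output, with code requesting the treatment difference |

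Both documents say Wilcoxon will be used once assumptions fail, so part of the ambiguity starts in the protocol. The protocol settles it with its supportive-only sentence. The SAP does not repeat that sentence.

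**2. Size of the opening**

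From the documents: two-sided 5% level; 36 evaluable and 44 enrolled patients; two periods, two sequences. The documents give no variance (protocol 14.1), so all distributions below are assumed.

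For each patient, d = value at dosing visit 1 minus value at dosing visit 2. The treatment test compares d between sequences: t test on raw d, t test on d of log(x+0.1), and Wilcoxon rank-sum on raw d. With complete pairs the raw t test is the mixed-model treatment test. In one simulated data set (18 per sequence, 34 degrees of freedom) both gave t = −3.184.

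- *Set A:* log-normal percentage time, median 5%, capped at 100%; between-patient log-SD 0.9; within-patient log-SD 0.5, 0.7 or 0.9; zeros in 0% or 10% of visits in both arms; n = 36 or 44. That is 3 × 2 × 2 = 12 settings.
- *Set B:* n = 36, within-patient correlation 0.5; one normal, two log-normal and one log-normal-with-zeros distribution.

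Each null setting used 20,000 trials, except that the residual-driven rule in set B used 5,000. The simulation standard error near 5% with 20,000 trials is √(0.05 × 0.95 / 20,000) = 0.15 percentage points.

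| Which test decides | Type I error, set A | Type I error, set B |
|---|---|---|
| Raw model always | 3.7–4.6% | 3.4–5.1% |
| Wilcoxon replaces raw only if raw and log residuals both fail | 3.8–4.9% | not run |
| Each step replaces the last, on residuals alone | 4.9–6.6% | 5.1–6.0% |
| Raw or Wilcoxon, whichever is significant | 5.9–7.2% | 6.1–6.4% |
| Any of raw, log, Wilcoxon | 8.2–9.9% | 7.2–9.1% |

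A repeat of set A gave 3.7–4.7%, 6.1–7.3% and 7.7–9.8% for the first, fourth and fifth rows. In set B the lowest any-of-three figure (7.2%) is the normal case; the skewed cases give 8.1–9.1%.

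The fourth row can be checked by hand: P(raw or Wilcoxon) = [P(raw) + P(Wilcoxon) + P(they disagree)] / 2. For the first log-normal case in set B this is (4.08 + 4.81 + 3.68) / 2 = 6.29%, the simulated value.

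**3. Would the choice change the conclusion?**

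With set A type data and a true ratio of 0.7 (active/placebo zeros of 0/0, 10/5 or 20/5%), raw and Wilcoxon disagree on significance in 15–25% of trials. Wilcoxon alone is significant in 12–23% and raw alone in 1–4%. With Shapiro-Wilk at p < 0.05 standing in for the qualitative review, raw residuals fail in 87–98% of null trials (62–86% at p < 0.001). Under these assumptions the fallback would often come into play. The SAP's own trigger has no numerical form, so these rates are only indicative.

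**The case against.** The strongest reply is that the hierarchy is already fixed. Protocol 14.4.3 makes alternate analyses supportive, and Wilcoxon is naturally one of them. The SAP says it is based on the protocol and revokes nothing. SAP 15.1.3 and 7.4 point to one primary analysis. The list of tables has an untransformed ITT analysis (14.2.2.1), a separate log analysis (14.2.2.3) and no Wilcoxon table. The change form of 8 May 2014 speaks of the primary analysis model in the singular. The phrase that Wilcoxon represents the comparison need not mean replacement, since the protocol uses the same verb for the least-squares mean difference. All this stands, and it is why the documents favour the raw model.

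Three further points also stand. Protocol 14 says deviations will be included in the SAP but asks for no separate declaration, so a reader who infers an undeclared breach goes too far. The printed program is core code and may not be the whole of what is sent. And the trial is open-label with the endpoint on the CRF, so withholding one output cannot exclude result-aware choice.

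A reader might also infer that the SAP lets the sponsor take whichever test is significant, or that the trial's type I error is 6–10%. The documents do not support either: no text prescribes such a choice, and nothing shows that one was made.

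The reply does not remove the procedural point. The SAP sends the treatment result to those judging the assumptions, leaves the next steps to judgement, and does not say in its own text what status those steps have.

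**Conclusion.** The concern holds in a limited form. The untransformed mixed model is the better-supported deciding analysis, and under the assumed distributions its type I error is 3.4–5.1%. Replacing it by Wilcoxon on residuals alone also kept the level (3.8–4.9%). The level is clearly exceeded only if the result guides the choice: about 6–7% for raw or Wilcoxon, and about 8–10% at worst for any of three, under skewed distributions that are assumptions and not taken from the documents. These figures bound what selection among these tests could do; they do not predict what the sponsor would do. The point is worth fixing because the opening lies in the primary test and costs little to close.

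**What to change.** 1. Add to SAP 15.1.3, in line with protocol 14.4.3: *The untransformed mixed model decides the primary comparison whatever the residual review shows; the transformed and Wilcoxon analyses are reported as supportive.* If the sponsor prefers another deciding analysis, name that single analysis by amendment before database lock.
2. Base the assumptions review on residual diagnostics only, and document its outcome before the least-squares means and fixed-effect tests are released. The printed core code has no explicit residual request, so a diagnostics run has to be specified in any case.

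The cost is one sentence and one run. The freedom to switch is lost, and the raw model may have less power with skewed data: at n = 36, true ratio 0.7, within-patient log-SD 0.7 and no zeros (all but n assumed), raw 32% against Wilcoxon 45%. If that matters, the remedy is to name another analysis before lock. Step 2 only limits result-aware choice in this open-label trial; step 1 is the main safeguard.
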